14.1 Previous and concomitant medications

The medications recorded on the “Concomitant Medication Details” eCRF form will be used as data source.

All terms will be coded using the most current World Health Organization Drug Dictionary (WHO Drug) version at the time of database lock. Medications will be presented using the Anatomical Therapeutic Chemical (ATC) classification system. Numbers of patients with concomitant medications/ treatment procedures will be presented overall and by ATC 2nd level, preferred terms.

Missing or partial dates for medications will not be imputed. In the case where it is not possible to define a medication as prior or concomitant, the medication will be classified by the worst case; i.e. considered as both previous and concomitant.

- Previous medications are medications, other than trial treatments and pre-medications for trial treatment, which are taken before first administration of trial treatment.
- Concomitant treatments are medications, other than trial treatments, which are taken by patients any time on-treatment (on or after the first day of any trial treatment for each patient) or within 33 days after last dose of trial treatment.

14.2 Concurrent procedures

All concurrent procedures, which were undertaken any time on trial, will be summarized according to the CRF page “Concurrent Procedures”. Concurrent procedures will be classified by medical review.

Number of patient with concurrent procedures, i.e, those on-treatment procedures will be summarized per treatment arm and overall and by reason and preferred name.

All medication/ treatment procedures will be listed.

14.3 Anti-Cancer Treatment after Discontinuation

New anticancer therapy will be recorded for patients who discontinue from the treatment for reasons other than PD at the additional follow-up visits. The following summaries will be presented for anti-cancer treatment after discontinuation:

- Any anti-cancer treatment after discontinuation (yes/ no)
- Type of systemic therapy
- Anti-cancer treatment drugs after discontinuation, presented by preferred terms alphabetically

- Time to start of new anti-cancer treatment after discontinuation (months): derived as the duration from randomization to the earliest start date of anti-cancer drugs after discontinuation
- Best response

15 Treatment Compliance and Exposure

Population: Safety Analysis Set

The date of first drug administration will be taken from the “Tepotinib Administration Details” and “Sorafenib Administration Details” eCRF forms respectively. The date of last drug administration will be taken from the “Treatment Termination for Tepotinib” and “Treatment Termination for Sorafenib” eCRF forms respectively.

The extent of exposure to Tepotinib or sorafenib will be presented by the following summaries:

- Duration of therapy (weeks):

$$\text{Duration of therapy (weeks)} = \frac{\text{date of last dose} - \text{date of first dose} + 1}{7}$$

Interruptions, compliance, and dose changes are not taken into account for the calculation of duration of therapy.

- Cumulative dose (mg):

The cumulative dose per patient in a time period is the sum of the total dosage that the patient received.

- Dose intensity (mg/day):

$$\text{Dose intensity (mg/day)} = \frac{\text{cumulative dose (mg)}}{\text{duration of therapy (days)}}$$

- Relative dose intensity (%):

$$\text{Relative dose intensity (\%)} = \frac{\text{Dose intensity (mg/day)}}{\text{planned dose intensity (mg/day)}} * 100$$

It will be summarized as continuous variables and also categorized into groups as the following:

- < 60%
- 60% - <80%
- 80% - <90%
- 90% - 110%
- >110%

16 Endpoint Evaluation

16.1 Primary Endpoint Analyses

Population: mITT Analysis Set; PP Analysis Set as sensitivity analysis if less than 90% of mITT.

Definition of primary endpoint

The primary endpoint is Time-to-Progression (TTP) as assessed by IRC according to RECIST 1.1 (Eisenhauer EA et al, 2009).

TTP is defined as the time (in months) from randomization to the first observation of PD (as assessed by IRC). The earliest scan date of target/non-target/new lesions will be used as the date of an overall response.

$$\text{TTP (months)} = (\text{date of 1}^{\text{st}} \text{ PD} - \text{date of randomization} + 1) / 30.4375.$$

Start date of TTP:

- The date of randomization

Event date is the earliest date of the following events:

- Observed PD before the patient drops out. Overall response of “not evaluable” will be changed to PD if subsequent scan is a PD. PD data from “Overall response” in Assessment of Disease Based on Imaging eCRF will be used.
- PD assessed by imaging after the patient drops out. Imaging PDs collected in the “Survival Follow-Up / Progression Disease” eCRF will be used.

Censoring rules:

- Censored on the date of randomization if no baseline or post-baseline assessment.
- Censored at the date of death, if the patient died without documented PD.
- Censored on the date of last tumor assessment or the date of randomization, whatever occurs later, if:
 - Lost to follow-up / withdraw consent without PD observed (includes also patients whose last available radiological assessment is at least 42 days before data cut-off), or
 - No PD observed up to the cut-off date (administrative censoring)

An overview of event/censoring rules is given in table 2:

Table 2: General events/censoring rules

	Date of event/censoring	Censored
Events:		

Radiological PD observed before the patient drops out.	Date of PD	No
Radiological PD assessed after the patient drops out.	Date of PD	No
Censoring:		
No baseline or post-baseline assessment	Date of randomization	Yes
Lost to follow-up / withdraw consent without PD observed (includes also patients with a radiological assessment that is at least 42 days before data cut-off)	Date of last known tumor assessment or date of randomization, whatever occurs later	Yes
No PD observed up to the cut-off date (administrative censoring)	Date of last known tumor assessment or date of randomization, whatever occurs later	Yes
Died without documented PD	Date of death	Yes

Primary analysis

The primary analysis will test the equality of TTP between treatment arms in the randomized part of Phase II, based on the mITT population, applying a two-sided stratified log-rank test at a significance level of $\alpha = 10\%$, taking into account the strata used for randomization, i.e., baseline BCLC stage. IVRS strata other than the eCRF strata will be used.

The following null-hypothesis is tested by the Cox's proportional hazards model stratified according to strata used for randomization:

$$H_0: \lambda_{\text{experimental}}(t) = \lambda_{\text{control}}(t)$$

$$H_1: \lambda_{\text{experimental}}(t) = \theta \lambda_{\text{control}}(t), \theta \neq 1,$$

where $\lambda(t)$ represents the hazard at time t and θ the unknown constant of proportionality of hazards in the allocated treatment groups in the randomized part. Ties will be handled by replacing the proportional hazards model by the discrete logistic model. With this ties option the Score-test in the Cox's proportional hazards model is identical to the log-rank test:

```
proc phreg data=xxx;
    strata BCLC;
    model TTE*TTE_censor(1) = treatment / ties = discrete rl;
    ods output globaltests=logRank_TTE (where=(test='Score'));
    parameterestimates = HR_TTE ;
run ;
Where:
TTE_censor = 1 if censored, 0 otherwise
Treatment = 1 if in experimental arm, =0 if in control arm
TTE      = Time to event variable, for primary analysis it is TTP by IRC.
```

The hazard ratio θ and 90% CIs of Tepotinib compared to sorafenib will be calculated by Cox's proportional hazards model stratified by baseline BCLC (stage B vs stage C).

Kaplan-Meier curves (product-limit estimates) will be presented by treatment arm together with a summary of associated statistics (25th quintile, median and 75th quintile survival time, 2-months, 4-months KM estimates and estimates for every 2 months thereafter as applicable) including the corresponding two-sided 90% CIs. The CIs for the median will be calculated according to Brookmeyer and Crowley (1982), and CIs for the survival function estimates at above defined time points will be derived from the Kaplan-Meier estimates using the log-log transformation (CONFTYPE=LOGLOG in SAS PROC LIFETEST). The estimate of the standard error will be computed using Greenwood's formula. Comparisons of survival rates will be performed from a Z-test using estimates and standard errors derived from the Kaplan-Meier method and Greenwood's formula. SAS procedure LIFETEST will be used to obtain Kaplan-Meier estimates and plots.

Sensitivity analysis

An un-stratified Cox model will be fitted, by which the hazard ratio θ , the 90% CIs and p-value will be calculated.

Multivariate analysis will be performed with a stepwise selection to assess the effect of predefined baseline covariates, which are the subgroup variables in Section 10.2 (except for baseline tumor HGF and baseline biomarker variables measured in plasma).

The model selection is performed without fitting the treatment group in the proportional hazards model. The values 0.15 and 0.40 will be used as the p-value for entry into the model inclusion and p-value for staying in the model, respectively exclusion criteria.

```
proc phreg data=Eff_mITT ;
    class all-subgroup variables;
    strata BCLC;
    model TTE*censor(1)= all-subgroup variables /ties=discrete rl selection=stepwise
    slentry=0.15 slstay=0.40 details;
    ods output globaltests=logRank(where=(test='Score')) parameterestimates=HR;
run ;
Where:
slentry= boundary for p-value of Score test for inclusion, other values than 0.15 can be
considered
slstay= boundary for p-value of Wald test for exclusion, other values than 0.40 can be considered
```

Once the selection procedure is finalized the model will be refitted with the strata and the treatment group, plus the selected covariates.

```
proc phreg data=xxx;
    strata BCLC;
    class all-selected-covariates;
    model TTE*TTE_censor(1) = treatment all-selected-covariates / ties = discrete rl;
    ods output globaltests=logRank_TTE (where=(test='Score'))
    parameterestimates = HR_TTE ;
run ;
Where:
TTE_censor = 1 if censored, 0 otherwise
Treatment = 1 if in experimental arm, =0 if in control arm
TTE = Time to event variables, for primary analysis it is TTP by IRC..
```

Subgroup analyses will be performed separately for each of the predefined subgroup variables without stratification due to the potential low number of patients per subgroup category. Cox regression models will be fitted for TTP by IRC as the dependent variable and with a subgroup type, the treatment group assignment and with and without the treatment by subgroup type interaction as explanatory variables. Hazard ratio (including 90% confidence interval) of Tepotinib compared to sorafenib is computed per subgroup level. P-value for the interaction test (Likelihood Ratio test) will be provided together with the hazard ratios and confidence intervals of the interaction model parameter. Forest plots will be presented with hazard ratios and 90% CIs of treatment for the overall treatment effect and for each subgroup level.

Kaplan-Meier curves will be presented by treatment arm for each predefined biomarkers subgroups.

A cross table of TTP assessed by IRC vs TTP assessed by investigator will be summarized to check the consistency of two definitions. If the TTP assessed by IRC and the TTP assessed by investigator are at most 30 days apart, the two TTPs will be considered consistent.

TTP assessed by IRC assessed will be further explored considering the PP population if the number of patients in the PP population is less than 90% of the number of patients in the mITT population.

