In order to provide overall estimates of the treatment effect data will be pooled across centers. The factor center will not be considered in statistical models or for subgroup analyses because of high number of participating centers and the anticipated small number of subjects randomized in each center.

All **statistical tests** comparing treatment arms will be performed two-sided using a significance level of  $\alpha = 10\%$ , unless otherwise specified. If CIs are to be calculated, they will be two-sided with a confidence probability of 90%, unless otherwise specified.

**Continuous variables** will be summarized using descriptive statistics, i.e., number of subjects (N), mean, median, standard deviation, 25th and 75th percentiles (Q1, Q3), minimum and maximum. Confidence intervals will be presented where appropriate.

**Qualitative variables** will be summarized by means of counts and percentages. Unless otherwise stated, the calculation of proportions will be based on the sample size of the population of interest. Counts of missing observations will be included in the denominator and presented as a separate category.

In general, the last measurement prior to or on the day of randomization will serve as the baseline measurement.

Details of the statistical analyses will be defined in the SAP.

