### 9.5.2.2 Statistical Analysis of Primary Endpoint of Phase II

The primary endpoint of Phase II in this trial is TTP based on tumor assessment by an IRC. TTP is defined as the time (in months) from randomization to date of the observation of radiological PD assessed by an IRC. Death without radiological progression date will be censored. In subjects without a progression date or loss to follow-up at time of analysis, the time between the date of randomization and the date of last tumor assessment will be calculated and used as a censored observation in the analysis. In principle, all tumor assessment should be considered to determine and derive the date of radiological progression.

The primary analysis will test the equality of TTP between treatment groups, based on the mITT population, applying two-sided unstratified log-rank test at a significance level of 10%.

The following null-hypothesis is tested:

$$H_0: \lambda_A(t) = \lambda_B(t) \text{ versus } H_1: \lambda_A(t) = \theta \lambda_B(t), \theta \neq 1,$$

where  $\lambda(t)$  represents the hazard at time  $t$  and  $\theta$  the unknown constant of proportionality of hazards in the allocated treatment groups (MSC2156119J and sorafenib).

The HR (including 90% CI) of MSC2156119J compared to sorafenib will be calculated by Cox's proportional hazards model.

Kaplan-Meier survival curves (product-limit estimates) will be presented by treatment arm together with a summary of associated statistics (median survival time, 6-month, 12-month survival rate estimates and estimates for every 6 months thereafter as applicable) including the corresponding two-sided 90% CIs. The CIs for the median will be calculated according to Brookmeyer and Crowley, and CIs for the survival function estimates at above defined time points will be derived directly from the Kaplan-Meier estimates. The estimate of the standard error will be computed using Greenwood's formula. Comparisons of survival rates will be performed from a Z-test using estimates and standard errors derived from the Kaplan-Meier method and Greenwood's formula.

TTP will be further explored considering the ITT population, the PP population and pre-defined subgroups (see Section 9.4).

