16.2.1 Progression-free Survival (PFS) Assessed by Investigator

Progression Free Survival is defined as the time from first administration date to the date of the first documentation of objective progression of disease (PD) or death due to any cause, whichever occurs first. PFS data will be censored on the date of the last adequate tumor assessment for subjects who do not have an event (PD or death), for subjects with an event after two or more missing tumor assessments (i.e. 84 days). Subjects who do not have a baseline tumor assessment or who do not have any post-baseline tumor assessments will be censored on the start date unless death occurred on or before the time of the second planned tumor assessment in which case the death will be considered an event.

$$\text{PFS (months)} = [\text{date of event or censoring} - \text{first administration date} + 1] / 30.4375$$

The censoring and event date options to be considered for the PFS are presented in table 1.

Table 1: PFS Events/censoring rules

Scenario	Date of event/censoring	Outcome
----------	-------------------------	---------

Radiological PD observed within 12 weeks of the last valid tumor assessment or first treatment administration	Date of PD	Event
Death without previously confirmed PD is observed within 12 weeks of the first administration or the last valid tumor assessment	Date of death	Event
No baseline or post-baseline assessment	Date of first administration	Censored
Event after 2 or more missing assessments, including death which is not within 12 weeks of the first administration or the last tumor assessment, whatever occurs later	Date of last known tumor assessment or date of first administration, whatever occurs later	Censored
Lost to follow-up / withdraw consent without PD/death observed, including subjects with a last tumor assessment date >12 weeks prior to the analysis cut-off date	Date of last known tumor assessment or date of first administration, whatever occurs later	Censored
Ongoing in the study without an event, that is, no PD/death event observed within 84 of the cut-off date from the last adequate tumor assessment for this still-in-trial subject (administrative censoring)	Date of last known tumor assessment or date of first administration, whatever occurs later	Censored

* Note: Not evaluable (NE) or Missing is not considered as a valid tumor assessment.

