16.2.2 Time-to-Progression (TTP) Assessed by Investigator

TTP is defined as the time (in months) from the date of first administration to the first observation of PD (as assessed by investigator):

$$\text{PFS (months)} = (\text{date of 1}^{\text{st}} \text{ PD} - \text{the date of first administration} + 1) / 30.4375.$$

Similar event/censoring rules will be applied except that the death will not be considered as a TTP event and instead will be censored at the last available tumor assessment. Analysis methods analogous to the ones for PFS will employed.

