16.2.5 Time-to-Symptomatic Progression (TTSP)

Time-to-symptomatic progression (TTSP) is defined as the time (in months) from the date of randomization to the date of deterioration of symptoms assessed by FHSI-8, defined as the total score increase by at least 4 points compared with the baseline value, or deterioration to ECOG PS of 4.

Start date of TTSP:

- The date of randomization

Event date is the date of the earliest deterioration.

Censoring rules:

- Censored on the date of randomization if no baseline or post-baseline assessment.
- Censored at the date of death, if the patient died without deterioration.
- Censored on the date of last FHSI-8 / ECOG assessment or the date of randomization, whatever occurs later, if:
 - Lost to follow-up / withdraw consent without deterioration observed (includes also patients whose last available FHSI-8 / ECOG assessment is at least 42 days before data cut-off), or
 - No deterioration observed up to the cut-off date (administrative censoring)

The FHSI-8 will be scored by the following scoring guideline (version 4):

FACT Hepatobiliary Symptom Index (FHSI-8)
Scoring Guidelines (Version 4)

- Instructions:*
1. Record answers in "item response" column. If missing, mark with an X
 2. Perform reversals as indicated, and sum individual items to obtain a score.
 3. Multiply the sum of the item scores by the number of items in the subscale, then divide by the number of items answered. This produces the symptom index score.
 4. As with all FACIT questionnaires, a high score is good. Therefore, a score of "0" is a severely symptomatic patient and the highest possible score is an asymptomatic patient.

Subscale	Item Code	Reverse item?	Item response	Item Score	
FHSI-8	GP1	4 -	_____	= _____	
	GP2	4 -	_____	= _____	
	GP4	4 -	_____	= _____	
	Score range: 0-32	C2	4 -	_____	= _____
		CNS7	4 -	_____	= _____
		HI7	4 -	_____	= _____
		Hep2	4 -	_____	= _____
		Hep8	4 -	_____	= _____
Sum individual item scores:				_____	
Multiply by 8:				_____	
Divide by number of items answered:				_____ =FHSI-8 score	

Analyses analogous to the ones of TTP will be performed.

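### Phase II SAP 16.1 censors IRC-TTP deaths without progression at the date of death; the last tumor assessment, the only censoring date in protocol 9.5.2.2, is the better primary rule

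*SAP*

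**What the plan says.** **Protocol 9.5.2.2.** "Death without radiological progression date will be censored"; that sentence names no date. The next one covers subjects without a progression date or lost to follow-up: the time from randomization to "the date of last tumor assessment will be calculated and used as a censored observation in the analysis". No other censoring date for TTP appears there. Section 9.5.1 adds: "Details of the statistical analyses will be defined in the SAP".

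**Phase II SAP 16.1.** A bullet reads "Censored at the date of death, if the patient died without documented PD", and Table 2 repeats it. The bullet before it reads "Censored on the date of randomization if no baseline or post-baseline assessment". All remaining censored patients, including those lost to follow-up, go to the later of last assessment and randomization. Investigator TTP (16.2.4) takes over the same methods. The sensitivity analyses vary stratification, covariates, subgroups and the per-protocol set, but not the censoring.

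**Phase II SAP section 9.** The legible list of changes covers the per-protocol set and the Kaplan-Meier time points. Part of the section is blacked out.

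**Phase Ib SAP 16.2.2.** For TTP, "the death will not be considered as a TTP event and instead will be censored at the last available tumor assessment".

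**The concern.** The Phase II rule treats two patients with the same scan history differently. If scans stop without progression and the patient stays alive, follow-up ends at the last scan. If the patient later dies, follow-up runs on to death, although no scan could have shown progression in between. Those extra weeks add to the risk set but cannot yield an event, so they make the hazard in that arm look lower. The effect cancels when both arms lose scans at the same rate. It does not cancel when one arm stops scanning earlier, which in an open-label trial cannot be ruled out.

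In addition, a death before any post-baseline scan satisfies both the randomization rule and the death rule. Two programmers could follow 16.1 faithfully and produce different datasets for the primary endpoint.

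**Working it through.** **1. The rules applied to example patients.** Take clean scans at weeks 6 and 12, a new therapy and no further scans, and a cut-off after week 30. Time is (days + 1)/30.4375.
- Alive at cut-off: censored at week 12, (84 + 1)/30.4375 = 2.79 months.
- Died at week 30, Phase II SAP: (210 + 1)/30.4375 = 6.93 months. Under protocol 9.5.2.2 as naturally read, and under the Phase Ib rule: 2.79 months.
- The same death in Phase II PFS (SAP 16.2.1) is 210 - 84 = 126 days after the last scan. That exceeds the 84-day window, so it is censored at week 12.
- Died on day 30 with no post-baseline scan: randomization or day 30, order not stated. No scheduled scan falls before week 6, so this choice barely alters a risk set. It matters only when early scans were missed and death came later.

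**2. The plan's own figures.** Freedman: (1.645 + 0.842)² × (1.6/0.4)² = 6.18 × 16 = 98.9, against the stated 100 events. With medians of 2.8 and 4.67 months and 12 + 6 months of accrual and follow-up, the mean event probability is 0.868, and 100/0.868/(1 - 0.174) = 139.5, against 140. A censoring date creates no events, so none of this changes.

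**3. Simulated average HR (tepotinib to sorafenib), true HR 1.** From the documents: sorafenib median TTP 2.8 months; scans 6-weekly to week 36, then 12-weekly; 17.4% drop-out, used as the balanced early-stopping rate. Assumed: exponential times; pre-progression death medians of 6.5 to 20 months; scan stopping uniform over 0-180 days; scans on schedule to ±5 days; administrative cuts of 1-7 or 0-10 months (33-42 events of 90, near the 40-event trigger) or 6-18 months (final analysis under 12-month accrual). Unstratified Cox.

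| Cut | Early scan stopping, sorafenib v tepotinib | Last assessment | Date of death |
|---|---|---|---|
| Primary | 17.4% v 17.4% | 1.00 | 1.00 |
| Primary | 30% v 10% | 0.96-1.00 | 0.99-1.04 |
| Primary | 10% v 30% | 1.00-1.03 | 0.95-1.00 |
| 6-18 months | 30% v 10% | 0.96-1.00 | 1.05-1.12 |
| 6-18 months | 10% v 30% | 1.00-1.04 | 0.89-0.95 |

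**4. Heavier stopping.** Here scans stop at 0.15 v 0.05 per month, death hazards are 0.02 to 0.107 per month, and there are 42-55 events of 90. At true HR 1, with more stopping on sorafenib, the death-date HR is 1.08-1.29 and the last-assessment HR 0.93-0.94. With more stopping on tepotinib they are 0.77-0.94 and 1.07-1.08. At the lowest death hazard the two rules err by similar amounts (1.08 v 0.93; 0.94 v 1.08); the death-date rule falls behind as mortality rises. If scans always continue to progression or death, the HRs differ by at most about 0.002.

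**5. Single trials of 90 at the primary cut, balanced arms.** Deaths without progression number 8-9 (20-month death median) or 20-24 (6.5-9 months). The ratio of death-date HR to last-assessment HR has a 5th-95th percentile range of 0.92-1.09 (20 months) or 0.86-1.16 (6.5 months). The two-sided 10% test result differs between rules in 1.4-4.5% of trials at HR 1 and 3.3-6.5% at HR 0.6. The unstated precedence alone changes it in 0.5-2.8% and 1.2-3.2%. With no early scan stopping, precedence changes it in 0.0-0.3% at HR 1.

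**The case against.** **The SAP may simply be filling a gap.** The protocol's death sentence has no date, details are delegated to the SAP, and the bullet and Table 2 agree. TTSP (16.2.5) has the same pattern, "Censored at the date of death, if the patient died without deterioration", so the choice may be deliberate. This stands. A reader might infer a flat contradiction or an undeclared change. The documents do not support that: applying the last-assessment date to deaths is the natural reading, but still an inference, and an entry in the blacked-out part of section 9 cannot be excluded.

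**Scans are meant to continue.** Protocol 8.1.5 and 8.3 require imaging after discontinuation until progression, death or new therapy. This stands in part. New therapy ends scanning by design. The continued-scan rule covers only discontinuation for reasons other than progression, so an investigator's call of progression that the IRC does not share also ends it. Deaths are still collected through three-monthly survival contact.

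**Precedence can be guessed.** Phase II PFS counts a death within 84 days of randomization as an event despite listing the same randomization bullet, and the Phase Ib PFS text has an exception for early deaths: "unless death occurred on or before the time of the second planned tumor assessment in which case the death will be considered an event". Both hint that the death rule prevails. But they decide event versus censoring for PFS and state no order for TTP. Most deaths with no scan come before week 6 anyway, so the gap is small.

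**The rates are assumed.** No document gives rates of early scan stopping by arm. The 6.5 months is median overall survival, so as a pre-progression death median it is an upper scenario for mortality. The planned test is stratified by BCLC stage and the simulations are not. All of this stands and limits the result to a range.

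**Conclusion.** The concern holds as a choice of censoring date that should be settled, with a minor gap in precedence. At the primary cut neither rule is clearly better, and the differences between them in single trials with balanced arms are sampling variation, not bias. The case for the last assessment rests on consistency (protocol as naturally read, Phase Ib SAP, the SAP's own rule for living patients) and on longer follow-up. If TTP is repeated at the final analysis, unequal scan stopping moves the death-date HR away from 1 by up to about 0.12 under the 30%/10% assumption, against about 0.04 for the last-assessment HR.

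Two stronger readings are not supported. One is that the rule undermines power or the 10% level. Events and sample size are untouched, and rejection at HR 1 with balanced arms was 10.5-11.3% under every rule. Only the heavier unequal stopping raised it, to 11.5-21% (death date) against 9-13% (last assessment). The other is that the rule favors tepotinib. The direction depends on which arm stops scanning earlier, and the documents do not say.

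**What to change.** In Phase II SAP 16.1 and Table 2, and so in 16.2.4, censor deaths without documented progression at the last tumor assessment, or at randomization if there is no post-baseline assessment. This matches protocol 9.5.2.2 and removes the overlap. Report the death-date rule as a sensitivity analysis.

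If the sponsor keeps the death date as primary, declare it in section 9, state which rule applies to a death with no post-baseline scan, and run last-assessment censoring as the sensitivity analysis. Either way, settle it before database lock.

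The cost is SAP wording, a small programming change and one extra analysis run; no new data are needed. TTSP (16.2.5) has the same unordered pair of rules and can be tidied at the same time, but that is peripheral.
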